STU#: STU00212891

PROTOCOL TITLE: The association between Sleep, Heart Rate Variability, and Anxiety following brain injury.

PRINCIPAL INVESTIGATOR:

[name], MS
 Medical Director, Brain Injury Medicine & Rehabilitation Program
 Rehabilitation Institute of Chicago
 [contact]
[contact]

VERSION DATE:

Version 1

STUDY SUMMARY:

Investigational Agent(s) (Drugs or Devices)	
IND / IDE / HDE #	
Indicate Special Population(s)	 Children  Children who are wards of the state  Adults Unable to Consent  Cognitively Impaired Adults  Neonates of Uncertain Viability  Pregnant Women  Prisoners (or other detained/paroled individuals)  Students/Employees
Sample Size	
Funding Source	
Indicate the type of consent to be obtained	 Written  Verbal/Waiver of Documentation of Informed Consent  Waiver of HIPAA Authorization  Waiver/Alteration of Consent Process
Site	 Lead Site (For A Multiple Site Research Study)  Data Coordinating Center (DCC)
Research Related Radiation Exposure	 Yes  No
DSMB / DMC / IDMC	 Yes  No

OBJECTIVES:

Aim: To investigate the association between heart rate variability, anxiety and sleep in the Brain Injury population using biosensors.

STU#: STU00212891

Hypothesis: We predict that decreased heart rate variability and poor sleep quality will be significantly correlated with higher self-reported anxiety following BI.

BACKGROUND:

- 1.1 Anxiety is a common problem after Brain Injury (BI). Anxiety has been associated with interference in rehabilitation following BI and worse functional outcomes. Dysregulation of mood, including anxiety are common following TBI¹. This is a result of the primary neuropathology, as well as secondary factors such as sleep disturbances and memory of the inciting trauma. Depression and anxiety after a TBI are associated with poorer cognitive, social, and functional outcomes.⁴

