Wearable Biosensors and the ActiGraph will be placed on the subject's non-dominant wrist. If the non-dominant wrist has motor impairment due to brain injury, then the ActiGraph will be placed on the dominant wrist. If both arms have motor weakness due to the brain injury, then the ActiGraph will be placed on the least affected extremity. The ANNE™ sensor system set will be placed on the patient's chest and finger. Sleep data will be obtained for seven consecutive nights. For anxiety, we will have a daytime, 5-10 minute epoch to measure heart rate variability, using ANNE ECG and skin temperature sensors, or manual temperature. We will measure overnight sleep, not during the day, with ANNE sensor accelerometer and ECG. Sleep log data will be extracted from the medical record.

Each subject will be randomly assigned a coded identifier. A list of the subjects' names and respective coded identifiers will be stored in a secure location on one of the co-investigator's encrypted and password protected computers at the Shirley Ryan AbilityLab. The data collected will be associated with the coded identifiers on a Microsoft Excel spreadsheet on one of the co-investigator's encrypted and password protected computer at the Shirley Ryan AbilityLab. Data will consist of sleep and heart rate variability data from the wearable biosensors, and sleep logs by nursing staff, self-reported sleep quality, anxiety and PTSD scales. The scales, HAD, DASS-21 and PCL-S, will be obtained on five separate occasions.

STU#: STU00212891

The subject will be monitored to ensure they are not experiencing an allergic reaction/skin irritation from the wearable biosensor system. If this is the case, the treating physician will be notified and they will determine whether or not the patient should continue with the study.

Sleep log data will be extracted from the Cerner electronic medical record of each patient and recorded in a Microsoft Excel spreadsheet with associated coded identifier. Data will be stored on one of the co-investigator's password protected and encrypted computer at the Shirley Ryan AbilityLab.

Data recorded will include: sleep data as measured by sleep logs, ActiGraph, ANNE™ sensor system; scores of the HAD, DASS-21 and PCL-S on five separate occasions. No long-term follow-up data will be collected. Post-hoc analyses will be performed on biometric data collected by the ANNE™ sensor system – including heart rate, temperature and movement.

Questionnaires

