1. *Karolinska Sleep and wake diaries*: Participants will be asked to maintain daily sleep logs for 7 consecutive days and to note bedtime, wake-up time, total sleep time, sleep latency, wake after sleep onset, naps, any unusual events during the day or night, any hot flashes per day (if female), and rating of overall sleep quality. The sleep diary will provide more detailed information of sleep quality.
2. *The Pittsburgh Sleep Quality Index (PSQI)*: This self-rated 21 item questionnaire assesses individual sleep habits (bedtime, morning rising time, sleep-onset latency, and night sleep duration), insomnia, and hypnotic use over a 1-month time interval. The PSQI has internal consistency and a reliability coefficient (Cronbach's alpha) of 0.83 for its seven components. The PSQI has been widely applied in a variety of clinical settings and epidemiological studies in many countries, because of its satisfactory
3. *The Berlin Questionnaire*: These questions were designed to identify adult patients who are likely to have sleep apnea. It asks about snoring behavior, wake time sleepiness or fatigue, and the presence of obesity or hypertension.
4. *Post-traumatic Stress Disorder Checklist*: To evaluate for symptoms of PTSD in our BI population, we will use the Post-traumatic Stress Disorder Checklist (PCL) which assesses self-reported PTSD symptoms within the past 1 month that correspond with the DSM-IV criteria and the Davidson Trauma Scale (DTS). These scales have been researched and validated for use in civilian and veteran populations.⁶ The PCL-S, "S" for specific, is a 17-item self-report measure covering the 17 DSM-IV symptoms of PTSD that specifies date and event of trauma.
5. *The Hospital Anxiety and Depression Scale (HADS)*: It is a self-reported scale used to measure symptoms of depression and anxiety within the past one week. Patients rate the frequency of these symptoms on a 4-point Likert-type scale. It has been validated in both medical and general populations, the HADS consists of 14 items total and is divided into the Anxiety subscale (HADS-A) and Depression subscale (HADS-D). The HADS has strong internal validity in the TBI population with good concurrent and discriminant validity with other self-report scales.⁴
6. *The Depression Anxiety Stress Scale (DASS-21)*: It is a self-report scale assessing levels of depression, anxiety, and stress over the previous week. Items are rated on a 4-point

STU#: STU00212891

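### Does the lack of study days for the five anxiety-scale administrations leave the recorded sleep week without a matching anxiety score?

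*Protocol*

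**What the plan says.** The single hypothesis (Protocol, Objectives) is: "We predict that decreased heart rate variability and poor sleep quality will be significantly correlated with higher self-reported anxiety following BI".

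Procedures Involved sets out the measurements:

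- Sleep: "Sleep data will be obtained for seven consecutive nights", taken overnight.
- Heart rate variability (HRV): "For anxiety, we will have a daytime, 5-10 minute epoch to measure heart rate variability", using the ANNE ECG.
- Anxiety: "The scales, HAD, DASS-21 and PCL-S, will be obtained on five separate occasions". The later list of recorded data repeats this: "scores of the HAD, DASS-21 and PCL-S on five separate occasions. No long-term follow-up data will be collected".

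Under Questionnaires, HADS (item 5) is described as "used to measure symptoms of depression and anxiety within the past one week". Of DASS-21 (item 6) the protocol says: "It is a self-report scale assessing levels of depression, anxiety, and stress over the previous week".

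The protocol gives no day, interval or anchor for the five administrations and no day for the HRV epoch. It contains no table of assessments.

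**The concern.** The hypothesis relates one week of sleep to anxiety, and both anxiety scales ask about one particular week. If that week is not the recorded one, the two sides of the correlation describe different periods, and anxiety that varies over days would pull the correlation towards zero.

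An analysis plan can choose among the scores or average them. It cannot create a score for a week that nobody was asked about, so the timing of collection is properly a protocol matter. The text would allow five scores in the first five days, when the best of them covers only four recorded nights. Read literally, it would also allow all five before the recording or well after it. The HRV epoch seems open in the same way.

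**Working it through.** The protocol has no figure of its own on this point to reproduce. The check has two parts: how many recorded nights each score covers, and what incomplete coverage costs.

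**1. Coverage**

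Inputs from the protocol: seven recorded nights, five administrations, one-week recall. Convention: day 1 is sensor placement and night n follows day n. A score on the morning of day d looks back over nights d-7 to d-1.

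| Day of score | 1 | 2 | 3 | 4 | 5 | 6 | 7 | 8 | 9 | 14 | 15 or later |
|---|---|---|---|---|---|---|---|---|---|---|---|
| Recorded nights covered | 0 | 1 | 2 | 3 | 4 | 5 | 6 | 7 | 6 | 1 | 0 |

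Place the five occasions on five different days within days 1 to 7. There are C(7,5) = 21 ways, sorted by the last day used:

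- Last day 7: C(6,4) = 15 placements, best coverage 6 of 7.
- Last day 6: C(5,4) = 5 placements, best coverage 5 of 7.
- Last day 5: C(4,4) = 1 placement, best coverage 4 of 7.

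None reaches 7 of 7, but 15 of 21 miss by one night. If day 8 is also available, 35 of the C(8,5) = 56 placements include it and match fully.

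**2. Cost of a partial match**

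All inputs here are assumptions, because the protocol gives none. Daily anxiety has covariance t + (1 - t)ρ^lag. The stable share t is 0.20, 0.35 or 0.50, and the day-to-day autocorrelation ρ is 0.3, 0.5 or 0.8, which makes nine settings. The reliability of one score is 0.8. Recall is treated as exact and uniform over the week.

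For a single score on day d:

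correlation with recorded-week anxiety = √0.8 × w(d)

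Here w(d) is the correlation between mean anxiety over nights 1 to 7 and over nights d-7 to d-1. For day 8, w = 1, so the correlation is √0.8 = 0.894. The observed correlation is then -0.40 times that value, taking -0.40 as the assumed true correlation.

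| Score used | w(d) | Correlation with recorded-week anxiety | Observed r |
|---|---|---|---|
| Day 8 | 1 | 0.894 | -0.36 |
| Day 7 or 9 | 0.958 to 0.991 | 0.857 to 0.886 | -0.34 to -0.35 |
| Day 6 | 0.892 to 0.966 | 0.798 to 0.864 | -0.32 to -0.35 |
| Day 5 | 0.815 to 0.931 | 0.729 to 0.833 | -0.29 to -0.33 |
| Mean of days 4 to 8 | | 0.90 to 0.95 | -0.36 to -0.38 |
| Mean of days 1 to 5 | | 0.66 to 0.86 | -0.26 to -0.35 |

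The loss from using day 7 instead of day 8 is at most 0.40 × (0.894 - 0.857) = 0.015. Using only the last score, 15 placements give at least 0.857, five give at least 0.798, and one gives at least 0.729. So 20 of 21 reach about 0.80 or more in every setting.

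For scale, the standard error of a correlation on Fisher's z scale is 1/√(n - 3). That is 0.10 at the 100 subjects named as the upper limit under Study Endpoints, and 0.29 at the 15 completers in the Participant Population(s) table. A shift of 0.015 is small against either.

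**3. Sensitivity**

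At reliability 0.7 the day-8 score gives 0.84. The mean of days 3 to 7, which includes no day-8 score, does better than that in 7 of the 9 settings. At reliability 0.8 it does better in 3 of 9. A full match is therefore not a condition for an equally good measure.

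**4. HRV epoch**

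The epoch uses the ANNE ECG, and its sentence comes directly after the placement of those sensors and the seven nights. The ordinary reading puts it in the wear period.

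**The case for a change.** The strongest case for a change is that it would cost only a line of wording and that a poor schedule could not be repaired afterwards. At the least favourable corner the loss is real. A mean over days 1 to 5 could show a true -0.40 as -0.26. At two-sided 5% and 80% power (assumed), n = (2.80 / atanh r)² + 3 gives 59 subjects for r = 0.36 but 114 for r = 0.26, which is above the limit of 100. The protocol ties the Actiwatch to the sleep diary explicitly (the ActiGraphy section) and makes no such link for the anxiety scales.

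Much of this is correct as fact. The days are missing, and the coverage counts are right. It carries less weight as a reason to change the plan:

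- The figure of -0.26 needs the one worst placement of 21, the worst of nine assumed settings, and averaging of all five scores. Taking only the day-5 score from that same placement gives at worst -0.29, or 92 subjects. A day-7 score gives at worst -0.34, or 66.
- Schedules with no overlap at all need every score on or before day 1, or from day 15 on. Scores that late sit poorly with an inpatient study that collects no long-term follow-up.
- Counting coverage to the night assumes exact recall. The Background says these patients are often amnesic, so the difference between 6 and 7 nights is finer than the instrument can resolve.

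**Conclusion.** The concern does not call for a change. The protocol leaves the days of the five administrations unwritten, but it fixes no bad schedule and contradicts nothing. A team spreading five administrations over a seven-day recording would in most cases have a score at or near the end of it. On the assumed inputs, a score one day before or after the best day costs at most about 0.015 on a true correlation of -0.40, and 20 of the 21 placements within the recorded week yield a last score correlating about 0.80 or more with the recorded week's anxiety. Which score or mean to use can be left to the analysis plan.

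This rests on the five occasions falling in or near the recorded week, which the text implies but does not state. It also rests on the assumed autocorrelation, stable share, reliability and exact recall. The HRV part does not stand, because the sensor used points to the wear period. What remains is an operational detail that a visit schedule or data-collection form would normally settle.

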Likert-type scale, with higher scores reflecting higher levels of depression, anxiety, or stress. The measure displays good-to-excellent reliability and validity.⁵

DATA AND SPECIMEN BANKING

Subjects will be assigned confidential codes for data collection. Code assignment will be kept separate from data information; subject code will be kept in a secure room under lock and key. No personal information will be stored with their data. Any data, photos or video will be stored for 7 years and stored on a secure, password protected computer at Shirley Ryan AbilityLab.

The data stored includes all information pertaining to the performance based outcomes measures and evaluations.

In the event this study will be published, data may be released to report the outcomes of this study. No released data will include identifiable information.

SHARING RESULTS WITH PARTICIPANTS

Results will be shared with participants if they request the information, but only after data analysis is complete. Results will only be shared among qualified research staff within Shirley Ryan AbilityLab and/or other Northwestern research labs. If the participant is interested in seeing the data collected, he/she will be given a summary of analyzed data. Research staff will explain and interpret the observations

INCLUSION AND EXCLUSION CRITERIA

Every patient admitted to the Shirley Ryan AbilityLab for rehabilitation following brain injury will be screened for the inclusion and exclusion criteria in order to assess their candidacy to participate in the study

Inclusion criteria:

- Subject must have had a brain injury
- Subject must be at least 18 years of age at the time of the injury
- The injury must have occurred in the past 6 months
- Subject must be medically stable – as determined by their ability to participate in acute inpatient rehabilitation

Exclusion criteria:

- Current use of beta blockers
- History of sensitivity or previous skin reactions to skin adhesives
- Non-English speaking
- Pregnant women
- Prisoners

This study will not exclude members of the following special populations: adults unable to consent.

This study will exclude individuals who are not yet adults, pregnant women, and prisoners.

STU#: STU00212891

VULNERABLE POPULATIONS

“[CHECKLIST: Cognitively Impaired Adults \(HRP-417\)](#)”

PARTICIPANT POPULATION(S)

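### The PSQI asks about the past month and eligibility sets no minimum time since injury, so a PSQI completed within 30 days of injury mixes pre-injury sleep into a post-injury measure

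*Protocol*

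**What the plan says.** Four parts of the protocol bear on this point.

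- **Objectives.** The hypothesis links low heart rate variability and poor sleep quality to self-reported anxiety, all after the brain injury.
- **Questionnaires, item 2.** The PSQI is a self-rated form on bedtime, rising time, sleep latency and sleep duration, and also "insomnia, and hypnotic use over a 1-month time interval". No day of administration is given, and the form is not tied to the injury.
- **Inclusion and Exclusion Criteria.** Time since injury has an upper limit only: "The injury must have occurred in the past 6 months". The nearest thing to a lower limit is "Subject must be medically stable – as determined by their ability to participate in acute inpatient rehabilitation", which is not a number of days.
- **Other instruments.** Actigraphy, sensor sleep recording and the sleep diary run for seven days or nights (Study Interventions 2.2; Procedures Involved; Questionnaires, item 1). HADS and DASS-21 ask about the previous week (Questionnaires, items 5 and 6).

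**The concern.** Patients are approached after admission to inpatient rehabilitation, and nothing in the protocol excludes someone injured two or three weeks earlier. Such a patient is asked about a month of sleep that began before the injury. The single PSQI score then combines sleep before the injury with sleep after it, in proportions that depend on how many days have passed.

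This has two consequences for analyses that use the PSQI as the measure of sleep after brain injury. If the pre-injury portion is unrelated to current anxiety or heart rate variability, it acts as noise and weakens the association. If days since injury is itself related to anxiety or heart rate variability, the changing mixture brings in confounding by time since injury. An analysis can adjust for days since injury or set early scores aside. It cannot separate pre-injury from post-injury nights within one score, because the recall period is fixed when the question is asked.

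**Working it through.** The protocol states no figure on this point, so there is none to reproduce. The check is simple arithmetic on the recall window.

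**Inputs**
- Recall window W: one month (Questionnaires, item 2), taken as 30 days, with 28 and 31 as checks.
- Days from injury to completion, t: not given in the protocol, so a range is shown. Eligibility allows any value up to 6 months.
- Recorded nights: seven (Procedures Involved).

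**Formula.** Pre-injury share of the window = max(0, (W − t)/W).

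| Days since injury at completion | W = 28 | W = 30 | W = 31 |
|---|---|---|---|
| 7 | 75% | 77% | 77% |
| 10 | 64% | 67% | 68% |
| 14 | 50% | 53% | 55% |
| 15 | 46% | 50% | 52% |
| 21 | 25% | 30% | 32% |
| 28 | 0% | 7% | 10% |
| 30 | 0% | 0% | 3% |
| 45 to 180 | 0% | 0% | 0% |

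Worked example: at day 10 with W = 30, (30 − 10)/30 = 0.67.

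**Where the pre-injury part is the larger part.** (W − t)/W > 1/2 means t < W/2. That is below day 14, 15 or 15.5 for W = 28, 30 or 31.

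**Later timing alone.** Suppose the one-month form is given at the end of the seven nights. A patient enrolled at day t then completes it at day t + 7, and with W = 30 the share is max(0, (23 − t)/30):
- day 7: 16/30 = 53%
- day 14: 9/30 = 30%
- day 21: 2/30 = 7%

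Later timing reduces the mixing but does not remove it.

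**Later timing with a past-week recall.** With W = 7 and completion at day t + 7, the share is max(0, (7 − t − 7)/7) = 0 for every t ≥ 0. The window is then the seven monitored nights.

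**Overlap with the recorded nights.** Even at the end of monitoring, the seven nights make up at most 7/30 = 23% of a one-month window. This holds for every patient, whatever the time since injury. It is a reason to align the windows, but it is not evidence of pre-injury content.

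**The case against.** Much of the case on the other side stands.

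- **How many patients are affected is unknown.** Patients must be stable enough for rehabilitation and already admitted, which implies some delay after injury. From day 30 to the 6-month limit there is no pre-injury content, and that is most of the eligible interval. A reader might infer that PSQI scores in this study will mostly describe the time before injury. The protocol does not support that, because it gives neither the distribution of days since injury nor the day of administration.
- **The PSQI is not shown to be the main sleep measure.** The aim is framed around biosensors, and Background 1.3 prefers sensors because these patients have difficulty recalling their sleep. The list of recorded data in Procedures Involved names sleep logs, ActiGraph and ANNE but not the PSQI. Self-reported sleep quality is mentioned elsewhere in that section and may mean the PSQI, but the diary also carries a quality rating. A reader might infer that the sleep-anxiety association as a whole is compromised. It is not: the seven-day sleep measures match the one-week HADS and DASS-21.
- **Sleep in the acute hospital is still sleep after the injury.** Only the part of the window before the injury conflicts with the hypothesis.
- **The PCL-S does not share the problem.** It too "assesses self-reported PTSD symptoms within the past 1 month", and a reader might infer that its scores also describe the pre-injury period. But the protocol describes a form "covering the 17 DSM-IV symptoms of PTSD that specifies date and event of trauma". If the injury is that event (the protocol does not name it), the symptoms cannot predate it. The PCL-S is given five times, but the spacing is not stated, so the overlap between its windows cannot be derived either. Nothing here calls for rewording it.
- **Analysis can help in part.** Adjustment or restriction by days since injury could be specified in an analysis plan that is not at hand. Restriction would be costly if the study completes with the 15 patients in the accrual table rather than the up to 100 under Study Endpoints.

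What remains is the mismatch in the PSQI itself, which arises when the data are collected.

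**Conclusion.** The point holds for the PSQI and is limited to it. A one-month recall with no minimum time since injury means that any PSQI completed within 30 days of injury contains pre-injury sleep, and below about day 15 mostly so. The share runs from 77% at day 7 through 30% at day 21 to zero at day 30. This takes a month as 30 days and counts every day in the window equally.

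The harm falls only on associations that use the PSQI as the measure of sleep after brain injury. Its size cannot be calculated, because the proportion of patients assessed before day 30 is unknown. The sensor, actigraphy and diary measures are unaffected. This is an inexpensive improvement to one questionnaire and does not threaten the main comparison.

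**What to change.** Give the PSQI once, at the end of the seven monitored nights, with the recall period set to the past week. Its window then matches the recorded nights and the one-week HADS and DASS-21, and contains no pre-injury sleep. Record days since injury at completion for every patient.

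If the one-month form is kept, do not treat scores completed under 30 days after injury as purely post-injury sleep. Report PSQI associations with and without those patients.

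The cost is one change to the questionnaire instructions and an IRB amendment. The past-week form is not the one whose alpha of 0.83 the protocol quotes, and its frequency response options need rescaling. The write-up should therefore describe it as a modified version.
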